		Pormat: Paper and pencil, Unline administration and scoring via PARiConnect, Software

		Age range: 2 years to 5 years 11 months
		Time: Annroximately 10-15 minutes to administer: 15-20 minutes
		to score
		Qualification level: B
		The BRIFF-P is the first standardized rating scale designed to
		specifically measure the range of executive function in preschool-
		aged children
		Eastures and benefits
		Measures multiple aspects of executive functioning: scales
		include Inhibit Shift Emotional Control Working Memory
		and Plan/Organize
		 Useful in assessing preschool-aged children with such medical
		acquired neurological and developmental conditions as
		prematurity, emerging learning disabilities and attention
		disorders language disorders traumatic brain injuries lead
		avance and porvasive developmental disorders (autism
		Test structure
		 A single Rating Form allows parents teachers, and day care
		nroviders to rate a child's executive functions within the
		context of his or her everyday environments—home and
		nreschool
		 Three broad indexes (Inhibitory Self-Control Elevibility and
		Emergent Metacognition) one composite score, and two
		validity scales (Inconsistency and Negativity) are provided
		Technical information
		 Normative data are based on child ratings from 460 parents
		and 302 teachers from urban suburban and rural areas
		reflecting 1000 II.S. Consus estimates for race/ethnicity
		renecting 1999 0.5. Census estimates for face/ethnicity,
		 Clinical samples included children with ADHD, prematurity
		- Chinical samples included chinaren with ADrib, prematurity,
		a mixed clinical group
		 Demonstrates high internal consistency reliability / 80- 95 for
		the parent sample and $90-97$ for the teacher sample) and
		moderate test-retest reliability (78- 90 for the narent sample)
		and 64-94 for the teacher sample)
		 Demonstrates convergent and discriminant validity with other
		measures of inattention hyperactivity-impulsivity depression
		atypicality, anxiety, and somatic complaints
		https://www.parinc.com/Products/Pkev/23
		BRIEF®
		Behavior Rating Inventory of Executive Function [®]
		Gerard A. Gioia. PhD. Peter K. Isquith. PhD. Steven C. Guv. PhD
		and Lauren Kenworthy. PhD
		Purpose: Assesses impairment of executive function
Parent (6-	Behavior Rating Inventory of	Format: Paper and pencil. Online administration and scoring via
17 years)	Executive Function [®] (BRIEF [®])	PARiConnect
		Age range: 5 years to 18 years
		Time: 10-15 minutes to administer: 15-20 minutes to score
		Qualification level: B
		Assess executive function behaviors in the school and home
		environments with the BRIEF, a guestionnaire developed for

	parents and teachers of school-age children. Designed to assess the abilities of a broad range of children and adolescents, the BRIEF is useful when working with children who have learning disabilities and attention disorders. traumatic brain injuries. lead
	exposure, pervasive developmental disorders, depression, and
	conditions.
	Features and benefits
	 Provides multiple perspectives. The Parent and Teacher
	Forms of the BRIEF each contain 86 items that measure
	different aspects of executive function.
	 Specific normative data based on age and gender. Separate
	normative tables for parent and teacher forms provide T
	developmental age groups by gender of the child
	 Nonoverlapping scales Theoretically and statistically derived
	scales measure different aspects of a child or adolescent's
	behavior, such as his or her ability to control impulses, move
	freely from one situation to the next, modulate responses,
	anticipate future events, and keep track of the effect of his or
	her behavior on others.
	lest structure
	 Eight clinical scales (Inhibit, Shift, Emotional Control, Initiate, Working Memory, Plan/Organize, Organization of Materials, Monitor) and two validity scales (Inconsistency and Negativity) give the clinician a well-rounded picture of the behavior of the child or adolescent being rated
	 The clinical scales form two broader Indexes (Behavioral
	Regulation and Metacognition) and an overall score, the
	Global Executive Composite.
	 The Working Memory and Inhibit scales differentiate among
	ADHD subtypes.
	Technical information
	Normative data are based on child ratings from 1,419 parents and 220 togethere from much suburban, and urban areas
	The clinical sample included children with developmental
	disorders or acquired neurological disorders (e.g. reading
	disorder, ADHD subtypes, traumatic brain injury, Tourette's
	disorder, mental retardation, localized brain lesions, high
	functioning autism).
	 High internal consistency (αs = .8098) and test-retest
	reliability (rs = .82 for parents, .88 for teachers) were found.

Test Administered to Children	4 years	5 years	6 years	7 years	8 years – 16 years	17 years
Wechsler Abbreviated Scale of Intelligence – 2nd Edition (WASI - II)						
N - Auditory Attention and Response*						
N - Inhibition*						
N - Comprehension of Instructions*						
N - Speeded Naming*						
N - Word List Interference*						
N - Narrative Memory*						
N - Design Copying*						
N - Theory of Mind						
N - Sentence Repetition						
N - Statue						
N - Word Generation						
Conners Kiddie Continuous Performance Test, 2 nd Edition (Conners K-CPT 2)						
Conners Continuous Performance Test 3 rd Edition (CPT 3)						
Child Administered Time Sub-total (Average Time ~ 90 minutes)	60	78	93	93	99	29
Test Administered to Parents for Children						
Strengths and Difficulties Questionnaire© (SDQ©)						
Behavior Rating Inventory of Executive Function [®] (BRIEF [®])						
Behavior Rating Inventory of Executive Function [®] – Preschool Version (BRIEF [®] -P)						
Parent Administered Time Sub-total (Average Time ~ 15 minutes)	15	15	15	15	15	15
Child/Parent Administered Total Time (Average Time ~ 105 minutes)	75	93	108	108	114	44

* Asterisk indicates N = NEPSY-II Core Assessment Battery; all else – Additional NEPSY-II Tests

Multi-site Study Child School Record Abstraction Form

Form Approved OMB No. 0923-XXXX Exp. Date xx/xx/201x

ATSDR estimates the average public reporting burden for this collection of information as 20 minutes per response, including the time for reviewing instructions, searching existing data/information sources, gathering and maintaining the data/information needed, and completing and reviewing the collection of information. An agency may not conduct or sponsor, and a person is not required to respond to a collection of information unless it displays a currently valid OMB Control Number. Send comments regarding this burden estimate or any other aspect of this collection of information, including suggestions for reducing this burden to CDC/ATSDR Information Collection Review Office, [name]; ATTN: PRA (0923-xxxx).

If the parent reports that the child has a developmental disability (e.g., ADHD, autism, or a learning disability), then ATSDR/[institution name] seeks to abstract the special education records for the child including the individualized education program (IEP), the IEP evaluation report ("Full Individual Evaluation" or "FIE"), and if available, the Independent Educational Evaluation. ATSDR seeks this information only if the child's parent or legal guardian has signed the consent to release student information.

ATSDR has received parental or guardian permission to obtain the specified school records for the child named below:

Name of Student (print):		Student ID No	Date of Birth: [mm/dd/yyyy]
Address of Student:			
City:	State:	_ Zip Code:	
Name of Parent or Guardian (print):			
Mail the completed form (using the enclose	ed pre-addressed re	turn envelope) to:***	
[name], PhD			
Agency for Toxic Substances and Di	sease Registry (ATS	DR)	
Division of Toxicology and Human H	lealth Science (DTH	IHS)	
[name]			
[name]			
[name]			

Does the student have one or more of the following disabilities?

DISABILITY	FINDING	IF YES,
Autism	Yes No	How diagnosed?
Developmental Disability	Yes No	Specify How diagnosed?
Intellectual/Cognitive Impairment	Yes No	Specify How assessed?
Sensory-Hearing, Vision, Deaf- Blind	Yes No	Specify
Neurological Disability	Yes No	Specify How assessed?

Attachment 18b.

Attachment 18b.

DISABILITY	FINDING	IF YES,
Specific Learning Disability	Yes No	Specify How assessed?
Attention Deficit Hyperactivity Disorder (ADHD)	Yes No	How diagnosed?
Social/Emotional/Behavioral Disorder	Yes No	Specify How diagnosed?
Adaptive Behavior	Yes No	Specify How diagnosed?
Language Disability	Yes No	Specify [] receptive [] expressive [] auditory processing How diagnosed?

Verbatim description of deficiencies noted in the Present Levels of Academic Achievement and Functional Performance (including deficiencies in social skills and behavior):

Note the following if found:

Services: Special Education	Yes No	Specify
Psychometric Test Results		IQ []

Attachment 18b.

	Reading Level []

Other Test Results:

Attachment 18b.

Multi-site Study Body and Blood Pressure Measures Report

STUDY ID No.:	NAME:				[
DATE: /	// TIME: :	AM PM			STAFF INITIAL:
BODY MEASURES AND BLOOD PRESSURE ARE USEFUL TO SEE IF YOU ARE AT RISK FOR DISEASES RELATED TO HIGH BODY FAT. ON THE BACK OF THIS REPORT READ MORE ABOUT WHAT YOUR MEASURES MEAN AND ACTIONS YOU SHOULD TAKE WITH A DOCTOR.					
YC	OUR BODY MEASURES		YOUR S	TATUS	
HEIGHT:	ft _ in	Body Mass Ind BMI and W. They can gauge your	lex (BMI) is calcu AIST SIZE are use risk for diseases	lated from h ful for meas that often o	eight and weight. uring body fat. ccur with more body fat.
WEIGHT:	_ Ibs	Examples are heart disease, high blood pressure, and Type 2 diabetes.			
BODY MASS INDEX:	kg/m²		Below 18.5 – 25.0 – 30.0 and A	BMI WEI0 18.5 Undo 24.9 Norr 29.9 Over bove Obes	GHT STATUS erweight nal see
WAIST SIZE:	in	Smaller Risk Larger Risk	WOM 35-in or More tha	EN ⁻ less n 35-in	MEN 40-in or less More than 40-in
YC	OUR BLOOD PRESSURE	YOUR STATUS			
SYSTOLIC over DIASTOLIC		SYSTOLIC over DIA Less than 120 AND Less 120-129 OR Less t 130-139 OR 80-89 140 or Higher OR 90 or	STOLIC than 80 than 80 Higher	BL	DOD PRESSURE CATEGORY Normal Elevated Hypertension Stage 1 Hypertension Stage 2
	/ mm Hg	Higher than 180 OR Higher	r than 120		Hypertensive Crisis

PLEASE TURN OVER AND READ MORE ABOUT HOW TO USE THIS INFORMATION

WHAT YOUR WEIGHT STATUS AND WAIST SIZE MEANS	WHAT YOUR BLOOD PRESSURE STATUS MEANS
Underweight or Normal	Normal
Most people who are underweight or at normal weight are not at risk for obesity-related disease. This is not a 100% surety because greater waist size, family history, or lifestyle choices still put some normal weight people at risk.	Your blood pressure is normal. You should still continue to have your regular appointments and check-ups with you doctor.
Overweight	Elevated
Overweight people with a smaller waist size are at increased risk of disease.	Your blood pressure is slightly above normal. You should still continue to have your regular appointments and check-ups with you doctor.
Overweight	HYPERTENSION NOTICE - Hypertension Stage 1 and 2
Overweight people with a larger waist size are at high risk for disease .	Your blood pressure is very high. You should call your doctor and ask for an appointment. Please take this form with you and show it to your doctor. If you do not have a doctor we will help to find you one.
Obese	HYPERTENSION NOTICE - Hypertension Crisis
People who are at the highest risk of disease . Please check with your doctor on how you could reduce your weight and waist size.	Your blood pressure is dangerously high. You cannot continue with the study. You should call you doctor right now and ask to be seen as soon as possible. Your doctor may want you to go to the emergency room instead of waiting for an appointment. Please take this form with you and show it to your doctor. If you do not have a doctor we will help to find you one.

THE NURSE HAS TO MARK WHICH CATEGORY APPLIES TO YOU BEFORE YOU LEAVE

Multi-site PFAS Health Study Advance Reporting Script for Clinical Tests

FOR OFFICE USE ONLY	
Adult Study ID No.	
Parent Study ID No.	
Child Study ID No.	

HELLO,

My name is ________ |. I am calling on behalf of the Agency for Toxic Substances and Disease Registry, or ATSDR for short. We are calling about the Multi-site PFAS Health Study. Am I speaking with |_NAME OF ADULT OR PARENT OF CHILD WHOSE RESULTS ARE CRITICAL |?

[IF NOT CORRECT PERSON] Please let me know the best time we can reach [him/her].

_____ (day of the week)

|--|

|__|:|__| AM PM (time).

I will call back then. Thank you.

[IF CORRECT PERSON] We are contacting you about [your/your child's] lab results. [Your/Your child's] [glucose/triglyceride/albumin/total bilirubin] test was significantly outside of the normal range. You should call [your/your child's] doctor today to discuss this. We will be sending you a letter with the details of [your/your child's] clinical tests.

Specifically, the results of [your/your child's] test have shown the following [read those that apply.]

Do you have a pen or pencil to write this down?

1. I am calling to report critical test results for |NAME OF ADULT OR CHILD.

2. Select the appropriate critical test and reporting value from below:

[Your/Your child's] glucose level was mg/dL. The test was performed on / / (date).
[If below 40 mg/dl read the following:] This is below the critical value of 40 mg/dL. [Your/Your child's] diabetes was poorly controlled or [your/his/her] medications might need to be adjusted. If this problem has not been addressed, we recommend that [you/your child] see the doctor immediately.
[If above 400 mg/dL read the following:] This is above the critical value of 400 mg/dL. [Your/Your child's] blood sugar was very high.

[Your/Your child's] triglyceride level was mg/dL. This is above the critical value of 1,000 mg/dL. The test was performed on _/ / / (date).
[You have/Your child has] a problem with lipid metabolism and have very high risk of heart disease.
[Your/Your child's] albumin level was g/dL. The test was performed on // / (date).
[If below 1.5 q/dL read the following:] This is below the critical value of 1.5 g/dL. You may have a liver or kidney problem.
[If above 7.9 g/dL read the following:] This is above the critical level of 7.9 g/dL. You may be severely or chronically dehydrated.

[Your/Your child's] total bilirubin was	mg/dL. This is above the critical value
of >12.9 mg/DI. The test was performed on _/ _	/ (date).

[You/Your child] may have a liver problem or a bile duct problem.

- 3. As a check, please read back the participant name and [his/her] critical lab result to me. > Verbally correct any errors and repeat the request for a "read-back" to verify accurate reporting and message received.
- 4. You should call [your/your child's] doctor today to discuss this information. As it is now more than |__| months since we collected [your/your child's] blood, this result may not be important today. You and [your/your child's] doctor may have already taken steps to correct the problem. We will be sending you a letter with the details of [your/your child's] clinical tests. If you or your doctor has a question about the results of these tests, you or he/she can contact

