Few studies have evaluated PFHxS exposures and the risk of cancers and other adult diseases. Although 9 10 epidemiological studies have primarily evaluated PFOA and PFOS, there remain considerable data gaps 11 concerning the health effects of exposures to these chemicals in adults. There have been inconsistencies 12 in findings across studies and limited sample sizes in some studies. For some adverse outcomes, only one or a few studies have been conducted. Finally, except for the C8 studies, there are no published individual-13 14 level epidemiological studies in adults that have evaluated the health effects from exposures to PFAS-15 contaminated drinking water. Therefore, additional research is necessary to determine whether drinking 16 water exposures to PFHxS, PFOS, and PFOA increase the risk of non-cancer diseases. The proposed scope 17 of the funding and sample size estimated for this health study would be too small and insufficient to evaluate cancer health outcomes. 18

19 **2.5.2 Hypotheses**

For children (aged 4-17 years), the Multi-site Study will evaluate the following main hypotheses, following
the outline of the biochemical analytical plan (**Attachment 2**):

22

23 Higher serum levels of PFOA, PFOS, PFHxS, or other PFAS are associated with:

- Lipids (higher total cholesterol, low-density lipoprotein, and triglycerides, and higher prevalence
 of hypercholesterolemia; higher prevalence of obesity).
- Impaired renal function (a higher level of uric acid, a higher prevalence of hyperuricemia, and a
 lower estimated glomerular filtration rate (eGFR).

1	3.	Liver function/damage biomarkers (alanine transaminase (ALT), γ -glutamyltransferase (GGT),
2		direct bilirubin, cytokeratin-18 (CK-18)), and non-alcoholic fatty liver disease/steatohepatitis.
3	4.	Glycemic parameters (glucose, insulin, glycosylated hemoglobin (HbA1c), auto-antibodies
4		[glutamic acid decarboxylase (GAD-65) and islet antigen 2 (IA-2)], C-peptide, pro-insulin) and
5		diabetes (type 1 and 2).
6	5.	Measures of thyroid function (differences in thyroid stimulating hormone - TSH, total thyroxin -
7		TT4, free thyroxin - FT4, and TT3; higher prevalence of hypothyroidism/hyperthyroidism).
8	6.	Differences in sex hormones, growth and sexual maturation (testosterone, estradiol, and sex
9		hormone-binding globulin (SHBG); insulin-like growth factor - 1 (IGF-1), age at menarche, delayed
10		puberty).

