21 The target areas for the Multi-site Study are those served in the present or past by public water systems 22 and/or private wells with documented past or present PFAS concentrations at the tap. The target 23 populations consist of those residing in households in the target areas. Those eligible for the study include 24 individuals aged \geq 4 years at the start of the study who reside in a household in the target area and 25 whose last exposure to PFAS-contaminated drinking water was no more than 15 years prior to the start 26 of the study. In addition to those who resided in households served by contaminated drinking water, 27 individuals exposed in utero and during breastfeeding when the mother resided in the household would 28 also be eligible if the exposure occurred within 15 years of the start of the study. The limit of 15 years 29 since last exposure was chosen to take into account the estimated half-lives in the body of PFOA, PFOS 30 and PFHxS and to ensure that exposures to the contaminated drinking water are relatively recent.

31

- Firefighters and others with occupational PFAS exposure from sources other than the drinking water will
 not be included in the study. In addition, children whose birth mothers had occupational exposures to
 PFAS from sources other than drinking water will be excluded. The goal is to enroll at least 2,000 children
- 4 (ages 4-17) and 6,000 adults aged \geq 18 years with drinking water exposure to PFAS.
- 5

6 **3.2.1 Children**

- 7 The eligibility criteria for children is as follows:
- 8 1. Aged 4 17 years at the start of the study,
- 9 2. Resided in areas with documented past or present PFAS drinking water concentrations at the tap,
- or were exposed in utero or during breastfeeding when the mother consumed the contaminated
 drinking water,
- 12 3. Drinking water exposure occurred within 15 years of the start of the study.
- Children will be excluded if their birth mothers were ever employed as a firefighter, ever
 participated in fire training exercises using AFFF foam, or were ever employed at industrial
 facilities that used PFAS chemicals in the manufacturing process.

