12 The questionnaire will request information on the child's height and weight, vaccination history, and 13 whether the child regularly exercises, currently smokes (and the number of cigarettes/day), or consumes 14 alcohol (and the number of drinks/week). The questionnaire will ask when the female child first began to 15 menstruate. The questionnaire will include specific questions addressing health outcomes of interest. 16 For example, for ADHD, the questionnaire will ask, "Has a doctor or health professional ever told your 17 child that your child has/had ADD or ADHD?" If the answer is "yes," a second question will ask for a list of 18 medications the child took for the condition. The questionnaire will ask if the child had learning or 19 behavioral problems, and if so, the type of problem and the treatment used. Questions would be included 20 for the hypersensitivity-related outcomes, asthma, atopic dermatitis (or atopic eczema), and allergies. The 21 study will attempt to confirm diseases and conditions reported in the questionnaire by accessing medical 22 records sending abstraction forms (Attachments 17&17a) to the medical care provider identified by the 23 participants on their consent forms (Attachment 7b5).

24 3.6.5.1.1 Child/Parent Neurobehavioral Assessments

25 **Table 3** provides the neurobehavioral test battery for children enrolled in the Multi-site Study.

26 Trained professionals will administer the following tests to children:

The Wechsler Abbreviated Scale of Intelligence – 2nd Edition (WASI – II) test will be administered
 to measure Full Scale IQ (FSIQ) among children 6-17 years (15 minutes). Intelligence testing of
 children aged 4 – 5 years will not be conducted.

- Each child 4-16 years will complete the NEPSY-II selected tests. Except for Theory of Mind, these
 additional tests are short and useful to assess memory and inhibition. For all the NEPSY II tests,
 children 4 years would take about 52 minutes, and children ≥5 years, about 70 minutes.
- Children aged 4 7 years will complete the Connors Kiddie Continuous Performance Test (K-CPT
- 5
- 2) (8 minutes), and children aged >7 years will complete the Connors CPT 3 (14 minutes).
- 6 Trained professionals will administer the following tests to parents about their children:
- Strengths and Difficulties Questionnaire (SDQ) (5 minutes).

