6 The adult participant or the parent of the child participant will receive a copy of the participant's Body 7 and Blood Pressure Measures Report (Attachment 19). These results will be immediately available and 8 will require no further evaluation or interpretation with two exceptions. The adult participant or the 9 parent of the child participant will receive a supplemental notice if the participant has a critical blood 10 pressure measure (diastolic blood pressure > 120 mm Hg, or systolic blood pressure >180 mm Hg). In this 11 case, a Critical Hypertension Notice will be appended to the Body and Blood Pressure Measurements Report along with written and verbal recommendations to obtain immediate medical attention. If the 12 participant does not have a personal physician, the study coordinator will provide a referral. If the 13 participant has an elevated but non-critical blood pressure measure (resting blood pressure > 140/90), an 14 15 Elevated Hypertension Notice will be appended to the Body and Blood Pressure Measures Report with written and verbal recommendations to obtain clinical follow-up. 16

- 17 3.6.6.1 Gift Cards as a Token of Appreciation for Participation
- 18 As a token of thanks for participation, the recipient will offer gift cards according to the following schedule:
- \$25 for body and blood pressure measures, and for blood and urine collection;
- 20 \$25 for completed questionnaire; and
- \$25 for child/parent completion of the neurobehavioral test battery
- Trained study staff will document provision of gift cards on the hard copy form (**Attachment 9**). As part of the exit procedures, the participant will sign this form to document receiving the gift card.

24 3.6.7 Adverse Events

The risks associated with this study are minimal. There is a small chance of unexpected or adverse events
 occurring during the course of this project. Unanticipated problems involving risk to the subjects or others

will be reported to the CDC Human Institutional Review Board (IRB) in accordance with institutional
 policies and procedures.

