Section F: Child's Medical History

F1. Have you ever been told by a doctor or other health care provider that your child has or had any of the following medical conditions? Fill out the table below. Circle appropriate response and ask the respondent to specify as directed.

м	edical condition		If yes, what year was your child diagnosed?
-		Yes (Please specify)	year
a. Ca	ancer?	No Don't know	
b. All	lergies?	Yes (Please specify) No Don't know	year
c. At	copic dermatitis/eczema?	Yes (Please specify) No Don't know	year
d. As	sthma?	Yes No Don't know	year
e. Ch (rł	nronic stuffy/runny nose hinitis/sinusitis)?	Yes No Don't know	year
f. Hi	gh cholesterol?	Yes No Don't know	year
g. Th	nyroid disease?	Yes (Please specify) No Don't know	year
h. De	elayed puberty?	Yes (Please specify) No Don't know	year
i. Ot	besity?	Yes No Don't know	year
j. Lu	ipus	Yes No Don't know	year
k. Ce	eliac disease	Yes No Don't know	year
l. Cr	ohn's disease	Yes No Don't know	year
m. Di	abetes	Yes, Type 1 Yes, Type 2 Yes, Type unknown No Don't know	year

	Medical condition		If yes, what year was your child diagnosed?
n.	Scleroderma	Yes No Don't know	year
0.	Attention deficit hyperactivity disorder (ADHD) or attention deficit disorder (ADD)?	Yes No → go to p Don't know → go to p	year
p.	How is your child treated for ADHD or ADD?		year
q.	Other learning or behavioral problems?	Yes (Please specify) No \rightarrow go to Question F2. Don't know \rightarrow go to Question F2.	year
r.	How is your child treated for their learning or behavioral problems?		

F2. What age was your child last vaccinated for:

Diphtheria, Tetanus, Pertussis ("DTaP")	age	Don't know	never was vaccinated
"Tdap" booster Tetanus, Diptheria, Pertussis	age	Don't know	never was vaccinated
Measles, Mumps, Rubella ("MMR")	age	Don't know	never was vaccinated
Tetanus shot (for a puncture wound or cut)	age	Don't know	never was vaccinated

FOR GIRLS ONLY

F3. Has your daughter ever used an oral contraceptive ("birth control pill")?

- ____Yes
- ___No \rightarrow go to Question F5
- ____Don't know \rightarrow go to Question F5
- ____Refused to answer \rightarrow go to Question F5

F4. When did your daughter last use an oral contraceptive ("birth control pill")?

___ Month/Year

F5. At what age did your daughter begin menstruation (have her first period)?

___Age

- ____Has not yet begun to menstruate \rightarrow go to Section G
- ____Don't know
- F6. Does your daughter's period occur regularly (every month)?

____Yes

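### Attachment 19 reports weight status to parents of children aged 4–17 on a single BMI scale with no age term, unlike the protocol's other result forms

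*Protocol*

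**What the plan says.** Section 3.6.6 of the protocol (Exit Procedures) states: "The adult participant or the parent of the child participant will receive a copy of the participant's Body" "and Blood Pressure Measures Report (Attachment 19"). It adds that the results need no further evaluation or interpretation, with two exceptions, both of which concern blood pressure.

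The form is the Body and Blood Pressure Measures Report. It comes just after Attachment 18b, and its title and Section 3.6.6 identify it as Attachment 19. Its weight-status table is broken in the extracted text ("WEI0 18.5 Undo 24.9 Norr 29.9 Over bove Obes"), which is not an error in the plan. The rows can still be read:

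- below 18.5: underweight
- 18.5–24.9: normal
- 25.0–29.9: overweight
- 30.0 and above: obese

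The waist limits are 35 inches for women and 40 inches for men. The blood-pressure categories are printed without an age limit. The reverse side explains each category, and a closing instruction requires the nurse to mark the one that applies before the participant leaves. The attachment list has one such form, with no child version.

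Section 3.2.1 sets the child age range at 4–17 years. Section 2.5.2 names "higher prevalence of obesity" as part of the first child hypothesis.

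**The concern.** The scale depends only on height and weight, so the same cut-points apply to a 4-year-old and to an adult. The waist limits have the same difficulty, since they are labelled for women and men. Staff following the form exactly must still assign a category to every child.

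What is at stake is what parents are told. The explanatory text says that most people in the underweight and normal categories are not at risk for obesity-related disease, with a caution about waist size, family history and lifestyle. A parent may take that message, or the word underweight, as a judgement about a child to whom the scale was never tailored. The study plans to enrol at least 2,000 children, and the form goes to the parent of each.

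**Working it through.** **1. What the scale does at child heights.** Attachment 13 records height in inches and weight in pounds, so BMI = 703.07 × lb / in². The weight at a given cut-point is cut × in² / 703.07. The heights and weights below are illustrations, not figures from the protocol.

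| Height, weight | BMI | Category on Attachment 19 |
|---|---|---|
| 40 in, 36 lb | 703.07 × 36 / 1,600 = 15.8 | underweight |
| 50 in, 57 lb | 703.07 × 57 / 2,500 = 16.0 | underweight |
| 50 in, 80 lb | 703.07 × 80 / 2,500 = 22.5 | normal |
| 55 in, 120 lb | 703.07 × 120 / 3,025 = 27.9 | overweight |

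Weight needed to be marked obese (BMI 30):

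- 40 in: 30 × 1,600 / 703.07 = 68 lb
- 50 in: 30 × 2,500 / 703.07 = 107 lb

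Weight needed to leave the underweight category (BMI 18.5):

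- 40 in: 18.5 × 1,600 / 703.07 = 42 lb
- 50 in: 18.5 × 2,500 / 703.07 = 66 lb

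This arithmetic needs no outside norm. Calling any of these children ordinary or heavy for their age does need one, and the protocol supplies none.

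**2. How the protocol's other forms treat age.**

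- Attachment 13 carries a blood-pressure chart of the same kind and labels it as a classification for adults aged 18 or older. Attachment 19 prints blood-pressure categories without that limit.
- Attachment 21, the clinical test report, has separate adult and child comparison columns.
- Attachment 2 gives separate child ranges for lipids and age-banded ranges for creatinine and hormones.

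Attachment 19 is out of line with these forms.

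**3. Whether the obesity sample size depends on the form.** Table 1 gives 250 per stratum from a prevalence of 17% and an OR of 1.88, with two-sided α .05 and power .80.

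- Second proportion: 1.88 × 0.17 / (1 − 0.17 + 1.88 × 0.17) = 0.3196 / 1.1496 = 0.278.
- Two-proportion size without continuity correction: 233 per stratum.
- With the Fleiss continuity correction: 251 per stratum, which reproduces the stated 250.

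The inputs are a planning prevalence and an odds ratio. No BMI cut-point enters the calculation.

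**The case against.** The strongest reply is that Attachment 19 is a feedback sheet and has no role in the analysis. That is right, and it limits the point. A reader might infer that the child obesity outcome is being counted with a BMI cut of 30, so that few younger children could be cases and power would fall. The documents do not support this, for four reasons:

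- Nothing in Section 3.10 or elsewhere makes the form's categories an analysis variable.
- Attachment 13 stores BMI as a number with no weight category. Height, weight, age and sex are all collected, so an age- and sex-specific classification remains open.
- Obesity is also collected by diagnosis. The child questionnaires (item F1) ask: "Have you ever been told by a doctor or other health care provider that your child has or had any of the following medical conditions", with obesity on the list. The child record abstraction form has an obesity item, and Section 3.6.5.1 says the "study will attempt to confirm diseases and conditions reported in the questionnaire by accessing medical" records.
- The outcome definition may properly sit in a statistical analysis plan that is not at hand, so its absence here is no finding.

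Any power loss would rest on an assumed lower prevalence, on an odds ratio carried over to a different case definition, and on a scoring rule the protocol does not contain. It should not be claimed.

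It can also be said that the Manual of Procedures, now a placeholder, may add instructions for children. It may, but the form and Section 3.6.6 as written already require a category for each child. That part of the concern stands.

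**Conclusion.** The point holds for the report form only. Attachment 19 applies one BMI scale, adult-labelled waist limits and blood-pressure categories without an age limit to participants aged 4–17. This is inconsistent with the way Attachments 13 and 21 separate adults from children. It is a matter of participant communication. It does not bias an outcome, and the 250 per stratum stands.

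The form reaches the parents of all enrolled children, planned at 2,000 or more. How many would receive a misleading category cannot be calculated from the documents, because that depends on child BMI norms they do not give. That young children commonly fall below 18.5 is likewise an assumption, although the weights needed to cross each cut-point follow directly from the form.

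**What to change.** Reconcile Attachment 19 with its use for children. Two routes would do so, and the choice belongs to the investigators:

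- limit the BMI, waist and blood-pressure categories to participants aged 18 and over, so that a child's report gives the measurements alone; or
- provide a child version with age- and sex-appropriate comparison values, as Attachment 21 already does for laboratory results.

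Section 3.6.6 should then name the version that parents receive. One added sentence should state that the form's categories do not define the child obesity outcome, which can be derived from the recorded height, weight, age and sex.

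The cost is a revision to one template and one or two sentences of protocol text. No new data, visits or sample-size changes are needed.
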